Document Nº: Protocol PMCF #200806	Page : 1 of 7	
Created : 01/02/2020	Version : 21/07/2024	

CLINICAL STUDY PROTOCOL

TITLE:

Post Market Clinical Follow up Study (PMCF) of CeraRoot Ceramic Implants One-piece: 3 Years Follow up (Period: 2020- 2023)

> ID:200806 NCT: 04598776

Written and Approved: [name]

NCT: 04598776	Protocol PMCF #200806	2/7

1.Description of study

1.1. Brief Summary:

The main objective is to evaluate the survival / failure rate of CeraRoot ceramic implants (one piece) during a three year follow up.

1.2. Detailed Description:

Traditionally the material of choice for dental implants has been titanium.

The success of such material has been unquestionable for the last decades.

However a number of issues arise lately regarding the biocompatibility or cytotoxicity or allergies regarding the degradation or oxidation particles within the bone or gum. Esthetics has been a concern as well, especially in patients with thin biotypes where the metal may produce a greyish look of the mucosa. For this reason the dental community and patients have raised much interest in ceramic dental implants as a tooth colored and metal free alternative for dental implants.

2. Objectives

Since 2006 CeraRoot ceramic implants have been available in the market. The main goals for designing this PMCF is to evaluate the long term success of CeraRoot ceramic implants. To achieve those objectives an observational study of patients that have received such implants is designed with implant survival as the main outcome measure.

3.Design

3.1. H₀ (Null Hypothesis)

There are no significant differences between the failure rate in this study and the failures rates in literature regarding this dental implant.

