3.2. H₁ (Alt. Hypothesis)

There are significant differences between the failure rate in this study and the failures rate in the literature.

3.3. Study Type:

Observational [Patient Registry]

3.4. Observational Study Model:

Cohort

3.5. Time Perspective:

Prospective

3.6. Biospecimen Retention:

None Retained

NCT: 04598776 Protocol PMCF #200806 3 / 7

3.7. Biospecimen Description:

3.8. Enrollment:

200 [Anticipated/ predicted]

175 real participants enrolled in the study.

3.9. Number of Groups/Cohorts:

1

3.10. Target Follow-Up Duration:

3 Years

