4.4. Sample Size Calculation

The sample size calculation has been performed with the assumption that the results of this study will be similar to those obtained in scientific literature with the same device which is around 98% (Oliva 2010).

The chosen statistical test and sample size equation for this clinical study is:

Formula:

$$n = P * (1 - P) * (\frac{Z_{1-\alpha} + Z_{1-\beta/2}}{|P - P_0| - \delta})^2$$

Source: The-Medical-Device-Sample-Size-Cookbook.pdf

Z values taken from this source.

The inputs required for this calculation are defined below

The inputs required for this calculation are defined below					
VARIABLE	VALUE	CLARIFICATION			
n	?	the sample size			
Р	2% (0,02)	This is called the True Proportion, i.e. the proportion to be tested. We assume that 2% of implants will fail to integrate.			
P0	3% (0,03)	This is called the Null Hypothesis Proportion. It's the reference value (gold standard) we are testing up against, and thus not assumed but originating from the literature			
P - P0	1% (0,01)	The minimum clinically meaningful effect, i.e. the difference between the two proportions - which makes it interesting to test for equivalence.interesting to test.			
δ (Delta)	8% (0,08)	The testing margin, if the difference in failures is 6% or more, it's not considered equivalent from a clinical perspective.			
H₀ (Null Hypothesis)	P - P ₀ ≥ δ	The difference between the two proportions is 6% or higher. This would mean that it's not equivalent.			

H ₁ (Alt.Hypothesi s)	P - P ₀ < δ	The difference between the two proportions is less than 6%, and thus equivalent.
α (Alpha)	5% (0,05)	The recommended minimum standard (can be lower)
Power (1 - β)	80% (β = 0,20)	The recommended minimum standard (can be higher)

The inputs in the formula are:

$$n = 0.02 * (1 - 0.02) * ((1.645 + 1.282) / ((0.02 - 0.03) - 0.08))^2 = 20.729 >> 21$$

This is, that we would need at least 21 subjects to illustrate equivalence of results of this clinical study versus the previous CeraRoot study (PMCF #191220). For this reason the estimated sample size of 200 patients for the present study PMCF 200806 is more than sufficient based on this statistical calculation.

5. Scientific Background

5.1. References:

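### Sections 3.1 and 3.2 state a no-margin test for a difference with agreement as the null, while section 4.4 chooses and sizes an equivalence test with agreement as the alternative

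*Protocol*

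**What the plan says.** Two pairs of hypotheses for the failure rate stand in the protocol.

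- **Sections 3.1 and 3.2.** H0: "There are no significant differences between the failure rate in this study and the failures rates in literature regarding this dental implant". H1: "There are significant differences between the failure rate in this study and the failures rate in the literature". No margin, level or numerical reference rate is given.
- **Section 4.4.** The text introduces its method with "The chosen statistical test and sample size equation for this clinical study is". H0 there reads "The difference between the two proportions is 6% or higher. This would mean that it's not equivalent", and H1 reads "The difference between the two proportions is less than 6%, and thus equivalent". Alpha is 5%, power is 80%, and the calculation ends at 21 subjects to show equivalence with an earlier study of the same device (PMCF #191220).

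The inputs to 4.4 are not single-valued. The margin is 8% in the value column and in the calculation, but 6% in the explanatory text. The reference rate P0 is 3%, described as "It's the reference value (gold standard) we are testing up against, and thus not assumed but originating from the literature", yet the same section assumes that "the results of this study will be similar to those obtained in scientific literature with the same device which is around 98" percent, which is a failure rate of about 2%. The endpoint in the P row is failure to integrate ("We assume that 2% of implants will fail to integrate"), while the primary outcome in section 3.12 is implant survival to 3 years.

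Section 3.8 records 175 participants enrolled. The version is dated 21/07/2024, after the 2020-2023 period in the title.

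**The concern.** Agreement with the reference is the null in section 3 and the alternative in section 4.4. Rejecting the null is therefore an unwelcome or at least discordant finding under one section and the success criterion under the other. A non-significant result under section 3 would invite the statement that the device performs as in the literature, although failing to detect a difference does not establish equivalence. The sample size justification gives that test no support, because it was built for the other one.

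The protocol itself states both pairs, so this is not detail left to the SAP: an SAP that followed either pair would contradict the other. With enrolment complete and two rules on file, a report could follow whichever suits the result.

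**Working it through.** **Inputs.** From section 4.4: P = 0.02, P0 = 0.03, margin δ = 0.08 or 0.06, alpha = 0.05, power = 80%, Z values 1.645 and 1.282. From section 3.8: N = 175. Because section 4.4 also puts the literature result at about 98%, P0 = 0.02 is shown as a second case. Assumed, because section 3 is silent: a two-sided 5% exact binomial test, in equal-tailed and minimum-likelihood form. Also assumed: one unit per patient, since implants per patient are not given.

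**1. The plan's own figure.** n = 0.02 × 0.98 × [(1.645 + 1.282) / (−0.01 − 0.08)]² = 20.73, rounded up to 21 (the protocol prints 20.729 and 21). The 21 thus reproduces with the signed difference used in the protocol's own line. The Z values are Z(1−α) and Z(1−β/2), the equivalence form. A two-sided 5% difference test with 80% power uses 1.960 and 0.842, so the 21 says nothing about section 3.

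**2. Sample size for the section 3 test at 2% against 3%.** n = [(1.960 × √(0.03 × 0.97) + 0.842 × √(0.02 × 0.98)) / 0.01]² ≈ 2,045. Exact power with 175 is 0.030 (equal-tailed) or 0.032 (minimum-likelihood).

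**3. Verdicts by number of failures, N = 175.** Equivalence is shown if the one-sided 95% exact upper limit lies below P0 + δ. That limit is 9% or 11% for P0 = 3%, and 8% or 10% for P0 = 2%.

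| Failures | Upper limit | p, P0 = 3% (equal-tailed / min.-lik.) | p, P0 = 2% (equal-tailed / min.-lik.) |
|---|---|---|---|
| 0 | 1.70% | 0.0097 / 0.0118 | 0.0583 / 0.0545 |
| 8 | 8.10% | not significant | 0.0508 / 0.0254 |
| 9 | 8.80% | not significant | 0.0182 / 0.0091 |
| 10 | 9.50% | 0.0787 / 0.0442 | 0.0059 / 0.0030 |
| 11 | 10.19% | 0.0344 / 0.0220 | significant |
| 12 | 10.87% | 0.0138 / 0.0069 | significant |
| 13 | 11.55% | significant | significant |

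The largest count that shows equivalence is 9 (6% margin) or 12 (8% margin) at P0 = 3%. At P0 = 2% it is 7 (the upper limit for 7 failures is 7.38%) or 10.

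- *Significantly different, yet equivalent.* P0 = 3%: 0 failures at both margins, and 11-12 (10-12 by minimum-likelihood) at the 8% margin. P0 = 2%: 9-10 (8-10 by minimum-likelihood) at the 8% margin, none at 6%.
- *Not significant, yet equivalence not shown.* Only at the 6% margin with the equal-tailed test: 10 failures at P0 = 3%, and 8 at P0 = 2%.

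**4. Probability that the verdicts disagree (equal-tailed / minimum-likelihood).**

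| True rate | P0 = 3%, δ = 6% | P0 = 3%, δ = 8% | P0 = 2%, δ = 6% | P0 = 2%, δ = 8% |
|---|---|---|---|---|
| 2% | 0.031 / 0.029 | 0.030 / 0.032 | 0.016 / 0.000 | 0.008 / 0.025 |
| 6% | 0.127 / 0.000 | 0.228 / 0.355 | 0.101 / 0.000 | 0.247 / 0.349 |

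At a true 2% with P0 = 3%, nearly all the disagreement is the zero-failure case: 0.98^175 = 0.029.

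**5. Non-significance when the true rate sits at the equivalence limit.** P0 = 3%: 0.077 / 0.042 at 9%, and 0.012 / 0.005 at 11%. P0 = 2%: 0.055 / 0.027 at 8%, and 0.007 / 0.003 at 10%.

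**The case against.** Section 4.4 names its procedure as the chosen test, and it alone carries alpha, power, a margin and a sample size, while section 3 is two generic sentences without a test. A reader could reasonably take 4.4 as governing. That stands as an indication of intent, but nothing in the text available withdraws 3.1 and 3.2, which remain the headed hypotheses of the design section.

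The section 3 test modelled here is a construction: the protocol gives it no level and no exact method. The results vary with those choices, and at a true 6% the disagreement runs from 0 to 36%. That is fair, and the figures should be read as a range under stated assumptions. The 3% power at 175 is partly a discreteness effect; at the planned 200 the equal-tailed exact power is 9%, which is also far too low.

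The table labels only 3% as P0, so the 2% case rests on the sentence about the literature result. It is shown for that reason and can be dropped once the reference is settled.

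Finally, the practical effect at the planning rate is small, about 3% of studies at P0 = 3%, mostly with no failures at all. This limits the weight of the point but does not remove the contradiction, which needs no calculation.

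**Conclusion.** The concern holds and should be fixed. The protocol states two opposed pairs of hypotheses, and its sample size supports only the equivalence pair. Confidence in the contradiction is high because it is on the page. The consequences are conditional on a two-sided 5% exact test and one binomial unit per patient with N = 175. Under those assumptions the verdicts disagree in 0 to 3.2% of studies at a true 2%. At a true 6%, three times the assumed rate but inside both margins, they disagree in 23 to 36% at the 8% margin and 0 to 13% at the 6% margin. The chance of a non-significant result at a rate on the equivalence limit is modest, 0.3 to 7.7%. The harm lies in an undetermined decision rule and in reading non-significance as similarity, not in a large error rate.

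**What to change.** Replace 3.1 and 3.2 with the equivalence hypotheses in two-sided form (H0: |P − P0| ≥ δ; H1: |P − P0| < δ) and state that they govern. Decide by whether the one-sided 95% upper confidence limit for the failure rate lies below P0 + δ. The lower side cannot fail, because P0 − δ is negative at every stated value (at the highest, 3% − 6% = −3%).

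For the rule to be usable, state one of each:

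- endpoint: the 3-year primary outcome of 3.12 fits the stated objective, whereas 4.4 describes failure to integrate;
- P0: 2% or 3%;
- comparator: the literature or study PMCF #191220;
- margin: 6% or 8%;
- unit: patient or implant.

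Date the change and disclose that it follows enrolment. If the margin and P0 cannot be shown to predate the data, report the result against all four limits: 2% + 6% = 8%, 3% + 6% = 9%, 2% + 8% = 10% and 3% + 8% = 11%.

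The cost is the rewording of two short sections, a sentence fixing the rule and its inputs, and a dated note, with documentary support for the margin and P0 where it exists. No new data or enrolment is needed.

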3.2. H₁ (Alt. Hypothesis)

There are significant differences between the failure rate in this study and the failures rate in the literature.

3.3. Study Type:

Observational [Patient Registry]

3.4. Observational Study Model:

Cohort

3.5. Time Perspective:

Prospective

3.6. Biospecimen Retention:

None Retained

NCT: 04598776 Protocol PMCF #200806 3 / 7

3.7. Biospecimen Description:

3.8. Enrollment:

200 [Anticipated/ predicted]

175 real participants enrolled in the study.

3.9. Number of Groups/Cohorts:

1

3.10. Target Follow-Up Duration:

3 Years

3.11. Groups and Interventions

no interventional

3.12. Outcome Measures

Primary Outcome Measure:

1. Implant Survival (Implant without pain, without mobility and in function.) [Time Frame: Baseline until 3 years]

Secondary Outcome Measure:

2. Surgical complications (SC)

Any complications, as bleeding, infection, no primary stability, early loss.... that may appear will be collected [Time Frame: Baseline to 7 days]

3. Before loading implants Complications (BLIC)

Any complications before the prosthesis is delivered (implant mobility, implant infection, implant loss...) will be collected [Time Frame: 7 days post operative to delivery of prosthesis]

4. After loading implants Complications (ALIC)

Any complications after the prosthesis is delivered (implant loss, bone loss, implant mobility...) that may appear will be recorded. [Time Frame: Baseline to 3 years]

5. Prosthetic Complications (PC)

Any difficulty during the confection of the crown, complications such as decementation, chipping, etc... will be registered. [Time Frame: Baseline to 3 years]

6. Implant Success

Implant survival in addition to not having bone loss around it.(. [Time Frame: Baseline to 3 years]

Definition of success:

A "successful implant" is an implant where all of the following success criteria (according to Buser et al., 1992) apply:

- Absence of persisting subjective discomfort such as pain, foreign body perception and/or dysesthesia (painful sensation);
- Absence of recurrent peri-implant infection with suppuration;
- Absence of tactile implant mobility:
- Absence of a continuous peri-implant radiolucency.

Definition of Survival:

Any implant present in the mouth at the moment of evaluation.

3.13. Eligibility

Study Population:

Patients that needed a tooth replacement that fulfilled the eligibility criteria.

Sampling Method:

Non-Probability Sample

Minimum Age:

18 Years

Maximum Age:

80 Years

Sex:

ΑII

Gender Based:

No

Accepts Healthy Volunteers:

Yes

Criteria:

Inclusion Criteria:

- Patients that have received the studied ceramic implant after 27 August 2020.
- Patients of CeraRoot Clinic (Barcelona)
- Age >18
- Single or multiple missing or hopeless teeth

Exclusion Criteria:

- · Smokers.
- The patient is taking medications or having treatments which have an effect on healing in general (e.g. steroids, large doses of anti-inflammatory drugs).
- Untreated periodontal conditions

4.3. Method

A patient history revision of dental charts is done by searching in the database patients with CeraRoot implants placed during the period of this study at CeraRoot CLINIC.

An excel sheet database is done with the patients that are compatible with the inclusion criteria. The statistical analysis is performed with the database.

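### The study period and the placement window in section 4.3 do not fit a 3-year outcome if they are the same span, and survival is not tied to 3 years after placement

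*Protocol*

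**What the plan says.** The title describes the study as "3 Years Follow up (Period: 2020- 2023", and the document header carries "Version : 21/07/2024". Section 1.1 sets the main objective: to "evaluate the survival / failure rate of CeraRoot ceramic implants (one piece) during a three year follow up". Section 3.10, "Target Follow-Up Duration", gives 3 years. The primary outcome in section 3.12 has "Time Frame: Baseline until 3 years".

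Section 4.3 selects cases by "searching in the database patients with CeraRoot implants placed during the period of this study". Section 3.13 requires placement after 27 August 2020 and gives no last placement date. Section 3.8 reports "175 real participants enrolled in the study", against 200 anticipated.

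At the end of section 3.12 survival is defined as "Any implant present in the mouth at the moment of evaluation", with no time attached. Section 4.4 works with one failure proportion: 2% expected, 3% reference, and a margin of 8% in the value column but 6% in the wording.

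**The concern.** The study period seems to do two jobs. In the title it is the span of the 3-year follow-up; in section 4.3 it is the window for placing implants. One span of roughly three years cannot be both. An implant placed late in the window has almost no follow-up when the window closes.

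The definition of survival does not settle this, because it looks at status on whatever date the implant is evaluated. An implant seen a few weeks after placement and one seen at three years would count alike. If all included implants then enter one proportion, the result averages over unequal follow-up and is not the quantity named in the main objective. At stake is the meaning of the headline survival figure.

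**Working it through.** **The plan's own figure.** Section 4.4, as printed: 0.02 × 0.98 × ((1.645 + 1.282) / (−0.01 − 0.08))² = 20.73, rounded up to 21. Follow-up time does not enter this formula, so the present point leaves that figure alone.

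**Inputs from the protocol.** Placement after 27 August 2020 (3.13); period 2020-2023 (title); outcome at 3 years (3.10, 3.12); 175 enrolled (3.8); expected failure 2% (4.4); version date 21 July 2024 (header), used only as an alternative cut-off.

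**Assumptions not in the protocol.** Even placement over the window, one implant per participant, and a true 3-year failure of 2%. Failure timing runs from a constant hazard to all failures spread evenly over the first 6 months.

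**Share reaching 3 years, placement to end 2023.** The window from 27 August 2020 to 31 December 2023 is 1,221 days.
- Cut-off end 2023: placement must be by 31 December 2020, which is 126 days. 126/1221 = 10.3%, and 175 × 0.103 = about 18 implants.
- Cut-off 21 July 2024: placement must be by 21 July 2021, which is 328 days. 328/1221 = 26.9%, or about 47 implants.

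**Expected simple proportion.** This is the average of F(t) over the follow-up times t, where F(3) = 2%. Under a constant hazard, h = −ln(0.98)/3 = 0.00673 per year and F(t) = 1 − exp(−ht). F is nearly linear here, so the average is close to 2% × mean follow-up / 3.

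*Literal reading (placement and cut-off both end 2023), failures counted to year 3 only.* Follow-up is uniform from 0 to 1221/365.25 = 3.343 years, capped at 3. Mean = (4.5 + 3 × 0.343)/3.343 = 1.654 years.
- Constant hazard: 2% × 1.654/3 = 1.10%; the exact average is 1.11%.
- All failures in the first 6 months: 2% × (1 − 0.25/3.343) = 1.85%.
- Largest shortfall: 2.00 − 1.11 = 0.89 points, and 175 × 0.0089 = 1.6 implants.

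*Same placement, cut-off 21 July 2024, capped at 3 years:* 1.41% to 2.00%.

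*No conflict.* With placement to 31 December 2020 and cut-off end 2023, every implant reaches 3 years. The proportion at 3 years is 2.00% whatever the timing of failures.

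*Follow-up beyond 3 years, later failures counted, constant hazard.*
- Placement to 21 July 2021, cut-off 21 July 2024: mean follow-up 3.45 years; 2% × 3.45/3 = 2.30%.
- Placement to end 2023, cut-off end 2026: mean follow-up 4.67 years; the exact average is 3.10%.

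The error can therefore go either way. On the fully literal reading it stays downward even without the cap (1.12% under a constant hazard).

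**Kaplan-Meier in place of the simple proportion.** The simulation used 20,000 runs, 175 independent implants and placement to end 2023. It covered three failure patterns: constant hazard, half of failures in the first 6 months, and all in the first 6 months.

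| Cut-off | Kaplan-Meier mean (%) | Kaplan-Meier SD (points) | Simple proportion SD (points) |
|---|---|---|---|
| End 2023 | 2.00-2.02 | 1.71 / 1.50 / 1.11 | 0.79 / 0.89 / 1.02 |
| 21 July 2024 | 1.98-2.00 | 1.35 / 1.25 / 1.05 | 0.88 / 0.96 / 1.05 |

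**The case against.** **The two periods may differ.** Section 4.3 gives no dates, and the title attaches its period to the follow-up. With placement starting in late August 2020, placement in 2020 and follow-up to 2023 is a natural reading, and it removes the conflict. The part of the protocol between sections 3.13 and 4.3 was not in the text read here and may hold placement or cut-off dates. This stands. A reader might infer that about 90% of implants never reached three years; the documents do not establish that.

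**No estimator is prescribed.** Section 4.4 is a sample-size section. It uses a single proportion but does not say that implants with short follow-up count as 3-year survivors, and the estimator may be set in a statistical analysis plan that is not shown. This also stands, so the absence of Kaplan-Meier from the protocol is not itself a fault. What remains is that the definition of survival, which the protocol does fix, carries no time point.

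**The direction is not fixed.** A reader might infer that a simple proportion always understates 3-year failure. That holds only if failures after year 3 are left out, and the survival definition does not leave them out.

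**Kaplan-Meier is not more accurate overall here.** At the end-2023 cut-off, combining bias and SD for the simple proportion gives √(0.89² + 0.79²) = 1.19 points under a constant hazard, against 1.71 for Kaplan-Meier. This is correct. The case for Kaplan-Meier is that it estimates the stated quantity and shows honestly how little was observed to year 3.

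**Conclusion.** The point holds in a limited, conditional form and is minor. In the text read here, the title period and the selection rule in section 4.3 do not fit a 3-year outcome if they are the same span. Survival judged whenever the implant is evaluated does not give a 3-year rate when follow-up differs.

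On the literal reading, a true 2% would appear as about 1.1% to 1.85%, an error of at most about 0.9 points or 1.6 of 175 implants. Section 4.4 describes the expected 2% as failure to integrate. If that means early failure, the shortfall is no more than 0.15 points. With longer follow-up and late failures counted, the figure could instead exceed 2%. All these sizes rest on assumed even placement, one implant per participant and the assumed failure timing.

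A reader might infer that the equivalence conclusion is undermined. The figures do not support that: 0.9 points is small beside a margin of 6 or 8 points. What is affected is whether the reported figure can be called a 3-year rate.

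**What to change.** 1. Reconcile the title period with section 4.3 by stating the first and last placement dates and the data cut-off, or by pointing to where the protocol already gives them.
2. Tie the survival definition in section 3.12 to three years after placement.
3. Report Kaplan-Meier 3-year implant survival, with each implant censored at its last recorded examination. Give a confidence interval that allows for several implants per patient, since section 3.13 admits patients with multiple missing teeth. If every implant is followed for three years, the estimate equals the simple 3-year proportion, so nothing is lost on the readings without conflict.

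Restricting the proportion to implants placed at least three years before the cut-off is not advised. It could leave only about 18 implants, below the 21 subjects that section 4.4 says are needed.

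The cost is protocol wording plus placement, failure and last-examination dates, which should be in the dental charts that section 4.3 already searches. The statistical downside is a wider interval: an SD of about 1.1 to 1.7 points against 0.8 to 1.0 for the simple proportion at an end-2023 cut-off, where only about 18 of 175 implants would be observed to three years. Those SDs assume independent implants; clustering within patients could widen them.
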